Who will not be excluded: Veterans with mild cognitive impairment, mild to moderate alcohol and substance use disorders, suicidal ideation without acute suicidality, and anxiety and depressive disorders will not be excluded because of their high co-occurrence with traumatic guilt [13-17] and recent findings that individuals with mild to moderate TBI can benefit from cognitive behavioral treatments [54]. We elected to allow Veterans to continue to engage in TAU other than trauma-focused treatments, as we do not expect TrIGR to be a stand-alone treatment for disorder specific conditions. Accordingly, all participants will be encouraged to continue to receive AUD/SUD and mental health treatment as needed, including pharmacotherapy, with their current providers throughout the study. TAU in both San Diego and Providence VAMCs consists of outpatient treatment for SUDs including relapse prevention using a

cognitive behavioral model, complementary groups such as relaxation training, sleep hygiene, and smoking cessation. Additionally, Veterans may be engaged in psycho-educational groups about PTSD (e.g., PTSD 101) that do not include trauma processing. Participants will be asked not to take part in any trauma-focused treatment such as PE, CPT, or Eye Movement Desensitization and Reprocessing (EMDR) during study participation. We will carefully track all treatment received during the active treatment and follow-up phases of the study and will evaluate whether differences in TAU are roughly equivalent across treatment groups and sites. If differences across sites exist, site will be included as a fixed effect in our analyses.

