9.5.2. Randomization. [name] will prepare the randomization table prior to the start of recruitment for each site. Randomization will be conducted separately at each site. We will use a permuted block randomization system, in which treatment assignment order is random within each block, with an equal number of participants assigned to each treatment. Block sizes will vary in random sequence between 2 and 4. We will stratify randomization by gender. We will evaluate successful randomization of other factors, such as symptom and substance use severity and demographics, and control for these factors if needed as described in section 9.11.2.

9.5.3. Feasibility of recruitment. VASDHS will serve as one of the two recruitment sites for the proposed research. We expect that three clinics within mental health services from which we will recruit heavily will be the PTSD treatment program, the Substance Abuse Mental Illness (SAMI) program, and the MST clinic. The PTSD clinic (which [name] formerly directed) completes over 50 new intakes with OEF/OIF/OND Veterans each month. During Q4 of FY2014, 540 OEF/OIF/OND Veterans with a PTSD diagnosis were seen for mental health services (either three or more sessions of psychotherapy or one medication appointment). The SAMI program has 34 OEF/OIF/OND Veterans enrolled in in the past three months. The program completes approximately 8 new intakes with OEF/OIF/OND Veterans each month. The MST Clinic sees approximately 18 new Veterans and 60 ongoing Veterans per month who are OEF/OIF/OND. We will have access to eligible participants based on the relationships and approvals we have already secured as part of Drs. [name] and [name]’s ongoing research programs and through their roles in the PTSD and substance use treatment programs at the San Diego VA. [name] current VA-

funded RCT is recruiting a similar population (although not limited to OEF/OIF/OND Veterans) and has been recruiting an average of 4-5 Veterans per month, 42% of whom (n = 33) are OEF/OIF/OND. Recruitment in the current RCT will be coming to completion as recruitment for the proposed study would be beginning, thus we will continue to receive a steady flow of referrals to our program of research.

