9.7.5. Standard Pharmacotherapy. In regard to pharmacotherapy, the VA follows treatment guidelines that require standardized prescribing practices for individuals with PTSD, depression, and AUD. We expect at least 85% of participants will be receiving medications based on these guidelines. We recognize that pharmacotherapy and changes in medications will be an uncontrolled source of variance but expect that any changes will be similar across treatment conditions and thus balanced by randomization. We considered recruiting participants who were not on medication or asking participants to be medication stable prior to study entry. However, psychotropic medications have well documented effectiveness for the treatment of PTSD, anxiety and depression and withholding such medication would be inappropriate for this high-risk population. Study coordinators will record from VA medical records and patient self-report all treatment (psychotherapy and medication) in which Veterans participate in the VA. Participants will also be asked about any treatment outside of the VA. We will compare treatment as usual between our two conditions and, if differences in any variables are found, include these as covariates in our analyses.

9.7.6. If Participants’ Alcohol/Substance Use Worsens During Treatment. If a therapist or assessor identifies worsening alcohol or substance use, the investigators will evaluate whether best clinical care indicates a need for more intensive SUD treatment. PIs will be contacted if a participant reports increased or risky substance use. If more intensive treatment is needed for any reason, we will assist in establishing treatment, then discontinue study participation following a final evaluation. Please see the Human Subjects section for the plan to address clinical worsening during study participation, including if participants display safety concerns such as suicidality or risk of violence.

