9.8.3. Treatment Process Measures. The Expectancy of Therapeutic Outcome (ETO), a 5-item self-report scale that evaluates treatment credibility, will be administered by the therapist in Session 1 after the therapist has provided the overall rationale for the treatment program. Questions are rated on a 0 to 8 Likert-type scale, with total scores from 0 to 32. The Additional Treatment Inventory (ATI) assesses additional treatment sought after the completion of study treatment. It asks about both psychiatric medications and psychotherapy. The Client Satisfaction Questionnaire [CSQ; 78] is an 8-item self-report scale measuring satisfaction with treatment. It has excellent internal consistency and correlates with therapists' estimates of client satisfaction. This instrument will be used to measure participants' satisfaction with the interventions.

Table 3. Measures

9.8.4. Medication Adherence. The ACTG Interview of Antiretroviral Medication Use (AIAM) will be used to assess medications that participants are taking and adherence to medication regimens. This interview was developed by the Adult AIDS Clinical Trials Group (ACTG) to assess in detail HIV medication adherence over the previous four days and takes about 10 minutes to complete [79]. The measure was modified for the current study to assess adherence for prescribed psychotropic medications by omitting references to HIV or AIDS and omitting the last item that lists side-effects that are common to HIV medications. The accuracy of self-reports of medication adherence has been questioned, and more objective methodologies are available, such as unannounced pill counts and medication bottle caps containing microchips that record medication adherence. However, for the current study, we have selected this self-report measure that requires less time, effort, and costs and has been validated when compared with other methods. Additionally, based on our prior research with Veterans, there are substantial differences in number and types of medications prescribed, complicating alternative non-self-report assessment procedures.

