9.10.1. Quality Control. Data Safety Monitoring will include periodic review and reporting of participant accrual, adverse event rates, treatment compliance, and drop-out rates. Study termination will be triggered by excessive drop-outs or adverse events. If treatment is needed during the follow-up phase due to increased substance use or serious psychiatric/medical symptoms, patients will be referred to appropriate treatment and followed by the PI and study psychiatrist until treatment is initiated. Adverse events will be reported to the DoD and VA IRBs and R&D (serious adverse events within 48 hours) and clinically managed as appropriate, including hospitalization if necessary. A summary of all adverse events will be submitted to the DoD annually. The PIs and a co-investigator (licensed psychologists in their respective states) will be available by pager 24-hours a day. The PI will be responsible for initial determination of serious adverse events from non-serious adverse events.

[name]. will serve as the medical monitor. Her functions include the following: (1) Review of research protocol and plans for data safety and monitoring; (2) Evaluation of the progress of the study every 6 months, including the quality of data collection, security and quality, participant recruitment/retention, participant risk and benefit, and any other factors affecting study outcome; (3) Consultation regarding continuation or termination or other modifications of the trial in the service of protecting safety of study participants; and (4) Evaluation of study adverse events and consultation to maximize protection of participants. Progress evaluations every 6 months will be provided to VA IRB, R&D, and HRPO, and study investigators. The medical monitor is not an investigator in the study and does not have any conflict of interest.

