9.11.1. Statistical Analyses. In the initial 3-6 months, data management procedures will be developed and put into practice. Data will be entered as it is collected and quality assurance checks conducted on an on-going basis (e.g., double entry and cross validation). Data analysis will be performed in multiple stages. In the initial stage, analyses will be conducted on an on-going basis to assure strict adherence to important issues for clinical trials, such as treatment fidelity, therapeutic alliance, and therapist effects. Next, preliminary analyses will be performed by examination of the distribution of variables to assess their characteristics (means, standard deviations, and skewness). Descriptive statistics and graphs will be used to summarize the characteristics of the study population. Continuous measures will be tested for normality and homogeneity of variance. Non-normally distributed variables will be transformed to meet the normal distribution assumption for linear models. Randomization will be assessed by performing a series of Wilcoxon-rank sum tests, ² or Fisher's exact tests to compare the groups on demographic and initial baseline clinical variables. Any variables on which the groups differ initially will be explored as covariates in subsequent analyses, as described in detail for each hypothesis, and we will take this into account in the interpretation of the outcome.

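### Section 9.7.5 makes any treatment-as-usual variable that differs between arms a covariate, with no time window; as written this reaches care received after randomisation, and sections 9.11.1 and 9.11.2 do not override it

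*Combined protocol and SAP*

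**What the plan says.** **Section 9.7.5** accepts that "pharmacotherapy and changes in medications will be an uncontrolled source of variance" and expects such changes to be balanced by randomisation. Coordinators record "all treatment (psychotherapy and medication) in which Veterans participate in the VA", and participants are asked about care outside the VA. The team will then compare TAU between the two conditions and, "if differences in any variables are found, include these as covariates in our analyses". No time window, criterion for a difference, list of variables, model form or named analysis is given.

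**What is recorded, and when.** Section 9.4 states: "We will carefully track all treatment received during the active treatment and follow-up phases of the study". It goes on to evaluate equivalence across treatment groups and sites, but its only modelling consequence concerns site differences. Section 9.8.3 adds an inventory that "assesses additional treatment sought after the completion of study treatment". Section 9.4 encourages participants to continue other care as needed. Section 9.10.1 provides for referral: "If treatment is needed during the follow-up phase due to increased substance use or serious psychiatric/medical symptoms", the patient is sent to appropriate treatment.

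**The statistical text is narrower.** Section 9.5.2 says the team will check other factors for balance and "control for these factors if needed as described in section 9.11.2". Section 9.11.1 states: "Any variables on which the groups differ initially will be explored as covariates in subsequent analyses"; the sentence then points to the detail under each hypothesis. It also makes all hypothesis tests intent-to-treat. Section 9.11.2 gives Hypothesis 1 a saturated treatment-by-time model, baseline covariates if the stage-one analyses call for them, and Site and Treatment by Site terms. Imbalances between arms within a site go to later analyses that check the conclusions. Hypothesis 2 uses a similar method.

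**The concern.** Care received after randomisation can be a consequence of assignment. A participant who improves may seek less outside care, and one who worsens may be referred for more. If such care differs between arms and is put in the model, the treatment coefficient no longer measures the total effect of being assigned to TrIGR rather than SCT, which is what an intent-to-treat test is meant to assess. Part of the effect may be removed, or an effect may appear where the total effect is nil.

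The trigger is also an observed arm difference, so the choice of model would be made after seeing trial data. One analyst could follow 9.7.5 and another 9.11.2, and they could report different results for Hypotheses 1 and 2.

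**Working it through.** The plan gives no figure for this point, so there is none to reproduce. The check has two parts: what the text covers, and what adjustment would do.

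**1. Scope of the rule.** Section 9.7.5 sets no time limit, speaks of changes in medication, and commits to including the variables rather than exploring them. Sections 9.4 and 9.8.3 do not set an arm-level covariate rule, but they show that the TAU data include care during treatment and follow-up. Section 9.5.2 refers its factors to 9.11.2; section 9.7.5 makes no such reference. That the rule covers post-randomisation care is therefore a reading, but the natural one.

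**2. Time-constant covariate.** Let D_t be the arm difference in guilt at visit t, Δ the arm difference in mean TAU, and b the fitted TAU coefficient. In a saturated treatment-by-time model with complete data, each D_t becomes D_t − bΔ.
- Change contrast: (D_last − bΔ) − (D_0 − bΔ) = D_last − D_0, so it does not move.
- Main effect averaged over visits: it moves by −bΔ.

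**3. TAU at post-baseline visits only.** The baseline difference is not adjusted, so the change contrast becomes D_last − D_0 − bΔ. A TAU-by-time term gives nearly the same result.

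**4. Illustration on assumed inputs.** From the power paragraph: 4 visits, correlations 0.2/0.5/0.8, and growth to 0.50 SD. Also used: 75 × 0.80 = 60 per arm after 20% attrition. Assumed: SCT participants receive q SD more TAU, each SD of TAU lowers post-baseline guilt by h SD, the total treatment effect is zero, and TAU is added when its arm difference has p < 0.05.
- Post-baseline-only shift = h × q, for example 0.4 × 0.5 = 0.20 SD.
- Main-effect shift with a time-constant covariate under compound symmetry = 0.75 × h × q, because TAU acts at three of four visits: 0.75 × 0.4 × 0.5 = 0.15 SD. With an estimated unstructured covariance it is 0.16/0.17/0.20 if always adjusted, and 0.14/0.15/0.17 under the rule, which fires in 77–78% of trials.

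Simulated type I error under the rule (4,000 trials per cell; Kenward-Roger correction and site terms not modelled; three values are for correlations 0.2/0.5/0.8):

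| q, h | Main effect, time-constant TAU | Change-contrast shift (SD), post-baseline-only TAU | Type I error, change contrast, post-baseline-only TAU |
|---|---|---|---|
| 0.3, 0.2 | 5.3–5.5% | 0.06 | 5.6/5.1/5.8% |
| 0.3, 0.4 | 7.5–7.9% | 0.12 | 5.8/6.9/9.2% |
| 0.5, 0.2 | 7.2–9.4% | 0.10 | 6.4/8.1/12.0% |
| 0.5, 0.4 | 24/19/19% | 0.20 | 12.3/16.5/34.3% |

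With a time-constant covariate the change contrast was unchanged in all 24 cells examined, with type I error 4.2–5.6%. A check with 20% random dropout agreed.

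**5. Direction.** Take a single endpoint with a true effect of −0.50 SD, TrIGR lowering outside care by 0.2 or 0.4 SD, and care lowering guilt by 0.2 SD per SD. The adjusted effect is −0.50 − (−0.2)(−0.2) = −0.54, or −0.50 − (−0.2)(−0.4) = −0.58. If a severity factor also drives both care and guilt with weight 0.5 each, the within-arm slope is −0.2 + 0.5 × 0.5 = +0.05, and the adjusted effect is −0.49 or −0.48. Type I error stayed near 5% in these scenarios.

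If care only follows earlier guilt and does not affect it, a true main effect of 0.25 SD becomes 0.20/0.19/0.17 when always adjusted with a time-constant covariate. The post-baseline-only change contrast does not shrink (0.49–0.53).

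**6. Chance difference.** If TAU differs only by chance there is no bias (type I error 4.4–5.6%). The rule can still fire easily: with k independent variables tested at 0.05, 1 − 0.95^k is 14.3% for k = 3 and 40.1% for k = 10. Both k and the threshold are assumptions.

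**The case against.** The strongest reply is that Hypothesis 1 would not move. It concerns greater reductions, section 9.11.2 interacts slope with treatment, and the power paragraph describes a difference growing from zero at baseline. All of this points to the change contrast, which an ordinary time-constant fixed effect leaves alone. The main-effect sentence in 9.11.2 explains how site heterogeneity is averaged and does not name the test. Unadjusted power for that effect in the simulation is only 58/39/31%, against the plan's 90%. All of that stands. However, the plan states no form for the TAU term, and care recorded by study phase could naturally enter as a time-varying covariate.

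A second reply is that the statistical section governs. Section 9.11.1 refers covariates to the hypothesis text, and 9.11.2 sends within-site imbalances to later analyses. Both lean that way, and if they govern, only a clarifying sentence is missing. But neither mentions TAU or section 9.7.5, and the imbalance sentence follows a discussion of balanced sample sizes.

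Third, differential care may be limited. Section 9.7.5 expects similar changes across arms, section 9.4 asks participants to avoid trauma-focused treatment, and section 9.7.6 ends participation, after a final evaluation, for those who need more intensive treatment. This narrows the route without closing it, since section 9.10.1 covers referral in follow-up.

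A reader might infer from the larger simulated error rates that the primary test is seriously inflated. The documents do not support this: those rates need assumed q and h, and either the main effect or a model form that the plan does not state. They also need a real TrIGR benefit that extra SCT-arm care exactly cancels.

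**Conclusion.** The point holds as a defect in the covariate rule and should be fixed. Section 9.7.5, as written, allows post-randomisation TAU into the analyses of Hypotheses 1 and 2, and nothing in 9.11.1 or 9.11.2 excludes it. If assignment affects that care, the adjusted estimate departs from the intent-to-treat effect in either direction and by an unknown amount.

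The consequence is conditional. It is nil for the change contrast with a time-constant covariate, and nil in expectation for a pure chance difference. It is possible for the overall main effect, and for the change contrast if TAU enters by visit, only after baseline, or with a time interaction. The sizes shown are illustrations, because the documents give no TAU parameters.

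Nor do the documents show a settled decision to adjust the primary model for post-randomisation care. They show two rules of different scope and no statement of which applies. Confidence is medium, because the reach of 9.7.5 rests on reading it with its own paragraph and section 9.4.

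**What to change.** Change the 9.7.5 sentence so that only TAU measured at or before randomisation may enter the primary models for Hypotheses 1 and 2, under the baseline-covariate rule already in 9.11.1 and 9.11.2. Say that post-randomisation TAU will be compared descriptively by arm and site.

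In 9.11.2, add that any model adjusted for post-randomisation TAU is supplementary, in line with the later analyses that section already provides for imbalances. State the form of the TAU term and the causal assumptions of any such model.

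The cost is one or two sentences in 9.7.5 and 9.11.2, with no new data and no change to sample size or clinical care.
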